## **Eligibility Criteria**

- 1) Volunteers who can read and sign the Research Information and Consent Form
- 2) Male and female adults, aged  $\geq 18$  years.
- 3) Presence of twenty or more (at least 2 posterior teeth in contact per quadrant, one of which is a molar), natural teeth in good state of repair with scorable surfaces.
- 4) Show evidence of chronic periodontitis, minimum of one site with PD  $\geq 5$ mm and BOP in at least two quadrants and no mechanical debridement for six months prior to the start of the study.
- 5) Agree to comply with the conditions and schedule of the study, i.e., willing to use the assigned products (see Treatment Phase and Standardize Oral Hygiene Instruction) according to instructions and be available for appointments.
- 6) Agree not to have a dental prophylaxis, professional whitening treatment, or any other elective, non-emergency dental procedure (other than those provided) at any time during the study.
- 7) Willing to refrain from using mouth rinses and tooth whitening products for the duration of the study.

## **Exclusion Criteria**

- 1) Any systemic conditions or medication intake that can alter periodontal status (e.g. uncontrolled diabetes (with <3-month recent HbA1c of  $>8.5\%$ ), anti-seizure medication, immunosuppressant, and calcium channel blockers with clinical sign of gingival overgrowth.
- 2) Immune-compromised state.

- 3) Any current heavy smoking habits (>10 cigarettes/day)
- 4) Any medical condition or history requiring prophylactic antibiotic coverage prior to dental treatment.
- 5) Females who are lactating or pregnant (as determined by medical history) or planning to become pregnant for the duration of the study.
- 7) Physical limitations/restrictions compromising oral hygiene procedures.
- 8) The presence of significant oral soft tissue pathology and/or lesions associated with ill-fitting appliances or restorations.
- 9) Tooth mobility associated with advanced periodontal disease (e.g. score of >2 using Miller Classification).
- 10) Any temporomandibular joint disorders.
- 11) Grossly carious, orthodontically banded, and third molars will not be included in the tooth count.
- 12) Presence of any significantly tipped, crowded, or largely defective restorations.
- 13) Any extreme adverse events relating to the use of HP gel (e.g. prolonged tooth hypersensitivity or aberrant soft tissue/mucosal reaction)

All participants were screened and evaluated at Loma Linda University School of Dentistry Graduate Periodontics Department. There are three groups of 20 patients, two therapy test groups and the control group.

### **Interventions**

The overall study was divided into three phases consisting of: 1) a therapy phase, 2) a treatment phase, and 3) a maintenance phase.

### **Therapy Phase**

The therapy phase consisted of establishing baseline periodontal parameters and implementation of standardized oral hygiene instructions. All subjects were given verbal and visual instructions and demonstrated whether or not they can perform adequate oral hygiene with repeated instructional sessions throughout the study (see Fig. 1). Oral hygiene instructions (OHI) included use of plaque disclosing agent and proper use of indicated oral hygiene aids. The remaining areas of disclosed plaque assessed the quality of oral hygiene. Subjects in the two therapy test groups were given their customized prescription tray along with supervised instructions during their first try-in. The therapy consisted of initiation of 1.7% HP gel delivered in these customized trays (Perio Protect Tray, Perio Protect, LLC, St. Louis, MO, USA) four weeks prior to non-surgical periodontal treatment, SRP, at week 0. Subjects were instructed to deliver the gel 2-times daily for 15 minutes. These subjects also received calendar journals and will be asked to log entries of when they have used their trays.

### **Treatment Phase**

The treatment phase began with non-surgical periodontal treatment. The two therapy test groups will have used their customized application HP gel for four weeks prior to the start of treatment. Non-surgical periodontal treatment consisted of 1-, or 2-visit SRP using ultrasonic and hand instrumentation with local anesthesia. Surfaces were to be deemed clean and debrided when subgingival deposits cannot be tactiley detected and the root surface feels smooth to the operator. Re-evaluation of SRP was done 8 weeks after the last session of SRP, at week 13. One therapy test group stopped using the HP

therapy at the re-evaluation visit (HP13). Whereas the other test therapy group received impressions for a new customized tray to continue application of HP therapy for an additional 13 weeks (HP26) to the termination of the study.

### **Maintenance Phase**

All subjects were recalled 4 weeks after re-evaluation of SRP was done for periodontal maintenance and again 3 months later for their final maintenance. In the HP26 group, subjects continued to use twice-daily HP gel for 15 minutes until the termination of the study, at week 26. Measurements for all subjects, correspondingly, were taken at week 26. Patients enrolled in the study were maintained with 3-month maintenance intervals for the duration of the study (See section Follow Up Care).

### **Standardized OHI**

Subjects were instructed to brush twice daily (morning and evening) with a dentifrice (Crest® Cavity Protection Toothpaste, Procter & Gamble Co., Cincinnati, OH, USA) and an adult, single end-tapered bristle toothbrush (Nimbus®Microfine®, Nimbus Dental, Los Altos CA). Patients will also perform interdental cleaning with aids including standard dental floss, threaded floss (Superfloss®, Oral-B®, Proctor & Gamble, Cincinnati OH), and interproximal brushes (Proxabrush®, TePe® USA, Anaheim CA) of varying sizes depending on embrasure sizes of the patient. Proper technique for each cleaning aid were demonstrated and reiterated at each appointment. Oral hygiene aids were dispensed to the patient four weeks prior to initiation of SRP. Patients have agreed

to refrain from the use of any prescription or over-the-counter mouth rinses and tooth whitening products.

### **Non-Surgical Periodontal Therapy**

All subjects received SRP by periodontal residents, either in their 2nd or 3rd year of specialty training, without time restriction. SRP was conducted with local anesthesia using ultrasonic instruments (Cavitron®, Dentsply® International, York PA) devices and hand instruments (Gracey Curettes, Hu-Friedy®, Chicago IL). Supra- and subgingival surfaces were determined “clean” when the surfaces felt smooth with the use of a periodontal explorer (11/12 After-Five™ Explorer, Hu-Friedy®, Chicago IL). Supragingival surfaces were polished with a rubber cup and polish paste.

### **Custom HP Tray Fabrication**

For subjects enrolled and assigned to the two test therapy groups, impressions of both maxillary and mandibular arches were made using polyvinyl siloxane (PVS) (Exafast™ NDS, GC America, Alsip IL) on stock plastic impression trays. Heavy viscosity vinyl polysiloxane (VPS) (Splash! ®, DenMat®, Lompoc CA) was used to first capture the dental arch and tooth surfaces then the resulting impression trays were impregnated with low viscosity PVS (Exafast™ injection). The impressions were sent to an FDA-registered dental laboratory for fabrication of custom, ethylene-vinyl copolymer trays (Perio-Trays®).

For subjects assigned to HP26, a second impression was taken at the re-evaluation appointment (Visit 5, Week 13) with the same methods as previously described. Once the

new tray was received from the dental laboratory, the patient was recalled and given the new custom tray along with any refills of HP gel.

### **Custom HP Tray Application**

The principal investigator supervised first use of trays and HP gel and, if needed, adjustment were made to trays so that it seated completely and comfortably in the subject's mouth while maintaining an adequate seal. Each subject applied a thin ribbon of gel throughout tooth indentations to provide a dosage of ~0.75 gram in each tray using a mass scale. Treatment frequency will be fixed throughout the study duration: Start of Treatment (Visit 2, Week 0) to 8-weeks following SRP (Visit 5, Week 13): two treatments per day, 15 minutes each

Subjects in the treatment groups documented tooth brushing and the gel tray applications in calendar journals for the entire duration of the study. Subject compliance was estimated throughout the study by reviewing diaries and by massing gel tubes at each visit. Patients were instructed to bring in their treatment tubes to each visit.

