### **Clinical Periodontal Parameters**

When collecting data, the examiner was blinded to treatment groups. Using the same PVS (Exafast™ NDS, GC America, Alsip IL) impressions to fabricate stone models

(Microstone, Whipmix Corp., Louisville, KY) a customized stent was fabricated using a positive pressure thermoplastic mold device (Biostar® Scan/Biostar® V, Great Lakes Orthodontics, New York). This 1-mm thick, semi-rigid stent was used as reference for the linear measurements using a periodontal probe (15 UNC Color-Coded Probe, Hu-Friedy, Chicago IL). All the measurement will be at 1 mm increments. Clinical parameter measurements was taken at six sites (mesio-buccal, mid-buccal, disto-buccal, mesio-lingual, mid-lingual, and disto-lingual) of each tooth. Relative gingival recession (R-REC) was measured from a margin of the stent to the most coronal height of the gingival margin. PD was measured as the distance from the gingival margin to the depth of the pocket. The probe was held flat against the tooth near the gingival margin and inserted into the periodontal pocket in a path that is parallel to the long axis of the tooth and advanced using light pressure until slight resistance is felt. Relative attachment level (RAL) was measured from a margin of the stent to the bottom of the pocket.

Bleeding on probing (BOP) was measured with sites that show any bleeding within 30 seconds of probing and was recorded as a percentage.

Oral hygiene level was measured by using the Modified Quigley-Hein Plaque Index (MQH) with disclosing solution that measures plaque on all teeth except 3rd molars at 4 surfaces on the buccal and lingual surfaces where:

Score 0 has no plaque

Score 1 has separate flecks of plaque along the cervical margin of the tooth

Score 2 has a  $\leq 1$  mm band of plaque at the cervical margin of the tooth

Score 3 has a band of plaque  $> 1$  mm but  $< \frac{1}{3}$  of the crown of the tooth

Score 4 has plaque that is covering  $\geq \frac{1}{3}$  but  $< \frac{2}{3}$  of the crown of the tooth.

Score 5 has plaque covering  $\geq \frac{2}{3}$  of the crown of the tooth

Full mouth series of periapical and bitewing radiographs was captured for all patients for standard periodontal diagnostic procedure as a part of the comprehensive periodontal evaluation. Radiographs of patients that were referred other clinics taken within a year of the comprehensive periodontal evaluation was used.

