## **Study Schedule**

A study schedule summary follows for HP group arms:

- Visit 1: Screening, recruitment, randomization and periodontal consultation was completed. PVS impressions were taken for fabrication of both prescription trays and customized stents created for clinical measurements if patient accepts and were recruited as subjects.
- Visit 2, Week 0: Data collected for clinical measurements with custom stents for RAL, PD and R-rec (Baseline). Delivery of prescription tray and first supervised instructions and placement of the gel for the treatment groups. OHI.
- Visit 3, Week 4: 4 weeks after the delivery of the tray and the gel; data collection of periodontal parameters with stent, 2 quadrants of SRP, reinforcement of OHI. Inquire if subjects had any adverse events with the use of hydrogen peroxide gel
- Visit 4, Week 5: No more than 1-week elapsed time since visit 4; SRP of 2 remaining quadrants, reinforcement of OHI.

- Visit 5, Week 13: Periodontal re-evaluation 8 weeks after last quadrant of SRP; data collection of periodontal parameters with stent, SRP on residual sites with detectable calculus, termination of peroxide use in HP13. For subjects enrolled in HP26 , new impressions were made for new prescription tray.
- (Visit 6, Week 14 [HP26 only]): New prescription tray delivery
- Visit 6, Week 17: Periodontal maintenance, reinforcement of OHI.
- Visit 7, Week 26: Data collection of periodontal parameters with stent (final exam), periodontal maintenance, reinforcement of OHI.

A study schedule summary follows for SRP arm:

- Visit 1: Screening, recruitment, and randomization. Data collection of periodontal parameters by residents and verified by attending periodontists. PVS impressions will be taken for fabricating of customized stents for clinical measurements if patient accept and are recruited as subjects.
- Visit 2, Week 0: Clinical measurements with stents (Baseline).
- Visit 3, Week 4: SRP and OHI
- Visit 3, Week 5: Remaining quadrants of SRP, reinforcement of OHI
- Visit 4, Week 13: Periodontal re-evaluation 8 weeks after last quadrant of SRP; data collection of periodontal parameters with stent, SRP on residual sites with detectable calculus, reinforcement of OHI
- Visit 5, Week 17: Periodontal maintenance, reinforcement of OHI
- Visit 6, Week 26: Data collection of periodontal parameters with stent, periodontal maintenance, reinforcement of OHI.

[figure not shown]

Figure 1. CONSORT Flow Diagram

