Figures 4, 5, 6, and 7 show baseline, 4-week, re-evaluation, and final MQH plaque scores. Plaque scores varied throughout the four timepoints with no obvious differences between groups.

[figure not shown]

Figure 5. Baseline MQH scores for A) SRP, B) HP13, and C) HP26

[figure not shown]

Figure 6. 4-Week MQH scores for A) SRP, B) HP13, and C) HP26.

[figure not shown]

Figure 7. Re-Evaluation MQH scores for A) SRP, B) HP13, and C) HP26.

[figure not shown]

Figure 8. Final MQH scores for A) SRP, B) HP13, and C) HP26.

[figure not shown]

Figure 9. Mean BOP in each group, SRP, HP13, and HP26

[figure not shown]

Figure 10. BOP % in pockets initially <5 mm

[figure not shown]

Figure 11. BOP % in pockets initially  $\geq 5$ mm

Figure 8 shows mean BOP. Baseline mean BOP was 45% for SRP, 57% for HP13, and 63.1% for HP26. At 4-weeks, mean BOP was 45% for SRP, 60% for HP13, and 44% for HP26. At re-evaluation, mean BOP was 37% for SRP, 30% for HP13, and 27% for HP26. Final mean BOP scores were 44% for SRP, 33% for HP13, and 28% for HP13. Mean BOP was significantly reduced in all groups between 4-week examination and re-evaluation with mean BOP scores at final examination staying similar to levels at re-evaluation for HP13 and HP26 groups. Mean BOP scores at final examination group for SRP group was similar to baseline.

Figure 9 shows BOP % in pockets initially  $< 5$ mm. At baseline, 24% of pockets  $< 5$ mm were BOP for SRP, 47% for HP13, and 52% for HP26. At 4-week examination BOP % were 29% for SRP, 44% for HP13, and 35% for HP26. At re-evaluation, BOP %

was 27% for SRP, 21% for HP13, and 22% for HP26. At the final exam, BOP % was 33% for SRP, 26% for HP13, and 22% for HP26.

Figure 10 shows BOP % in pockets initially  $\geq 5$ mm. At baseline, BOP % was 92% for SRP, 81% for HP13, and 91% for HP26. At 4-week examination, BOP % was 91% for SRP, 93% for HP13, and 83% for HP26. Re-evaluation BOP % was 91% for SRP, 78% for HP13, and 75% for HP26. At final examination, BOP % was 88% for SRP, 79% for HP13, and 78% for HP26.

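### Tooth-brushing diaries are described for the gel arms only, so unequal self-monitoring may contribute to the gel-versus-SRP difference in bleeding

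*Combined protocol and SAP*

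**What the plan says.** Chapter Two of the combined protocol and SAP describes the journal in two places, and the two do not match.

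- Custom HP Tray Application: "Subjects in the treatment groups documented tooth brushing and the gel tray applications in calendar journals for the entire duration of the study". On use of the records it adds: "Subject compliance was estimated throughout the study by reviewing diaries and by massing gel tubes at each visit".
- Therapy Phase, about the two test groups: "These subjects also received calendar journals and will be asked to log entries of when they have used their trays". Brushing is not mentioned there.

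No section describes a brushing diary for the SRP arm.

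Other parts of hygiene care are common to all arms. Therapy Phase gives every subject repeated instruction and uses disclosed plaque as the check: "The remaining areas of disclosed plaque assessed the quality of oral hygiene". Standardized OHI prescribes twice-daily brushing to everyone and has technique repeated at each appointment. MQH is among the assessments made by the blinded examiner. The Results chapter reports it for all three arms: "Plaque scores varied throughout the four timepoints with no obvious differences between groups".

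The Study Schedule lists the week-0 visit of the gel arms as "Delivery of prescription tray and first supervised instructions and placement of the gel for the treatment groups. OHI". The SRP list has only baseline measurements at week 0, and OHI first appears at week 4.

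Statistical Analysis names BOP reduction as a primary outcome (and lists BOP again as secondary). It describes no use of diary data or MQH in the BOP analysis.

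**The concern.** A log of tray use belongs to the intervention under test. A log of brushing does not, because brushing is prescribed to all three arms. Recording it in two arms only adds a co-intervention to the contrast: self-recording may prompt better brushing, and bleeding responds to home care. Randomization does not remove this, since the difference arises after allocation. Nor does the blinding, which covers the examiner only; SRP patients receive no tray and so know their arm.

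BOP is the outcome on which the Discussion claims a benefit. Two contrasts are most exposed:

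- **Weeks 0 to 4.** The second primary objective asks whether gel lowers inflammation before SRP. No arm has yet been debrided, so home care is the main competing explanation.
- **Weeks 13 to 26.** HP13 has stopped gel, but the tray-application section keeps its journal running. HP13 against SRP is then in part diary against no diary.

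**Working it through.** **1. Who keeps the diary.** The null hypotheses in the Introduction use the term treatment groups for all three arms, SRP alone included. In the tray-application section, however, the same sentence covers tray applications. Therapy Phase gives journals to the two test groups, and the Study Schedule ties that term to gel placement. Gel arms only is the natural reading. For the SRP arm it rests on silence.

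**2. What is logged and reviewed.** One section says tray use, the other says brushing and tray use. Review of diaries is stated to run throughout the study. The phrase about each visit clearly attaches to weighing the tubes and only arguably to the diaries.

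**3. Size.** The plan gives no diary effect and no power calculation, so there is no figure to reproduce. Inputs are the mean BOP percentages in the Results chapter (re-evaluation = week 13, final = week 26). The final 28% is printed as HP13 and is read here as HP26.

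| Arm | Wk 0 | Wk 4 | Wk 13 | Wk 26 | Change 0–4 | Change 13–26 | Change 0–26 |
|---|---|---|---|---|---|---|---|
| SRP | 45 | 45 | 37 | 44 | 0 | +7 | −1 |
| HP13 | 57 | 60 | 30 | 33 | +3 | +3 | −24 |
| HP26 | 63.1 | 44 | 27 | 28 | −19.1 | +1 | −35.1 |

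Difference from SRP in change from baseline:

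- HP13: −24 − (−1) = −23 points
- HP26: −35.1 − (−1) = −34.1 points

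Assume a diary effect of 2 to 5 BOP points (not in the documents). Its share of each difference is:

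- HP13: 2/23 = 9% to 5/23 = 22%
- HP26: 2/34.1 = 6% to 5/34.1 = 15%

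**4. The two exposed windows.** In weeks 0 to 4 both test arms have gel and journal. Relative to SRP they changed by +3 (HP13) and −19.1 (HP26): arms managed alike moved in opposite directions. In weeks 13 to 26, HP13 minus SRP is 3 − 7 = −4 points, small enough for a diary effect in the assumed range to matter.

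**5. Could the data settle it?** Use power = Φ(δ / (σ√(1/n₁ + 1/n₂)) − 1.96), two-sided 0.05, with δ = 5 to 10 points and σ = 15 to 25 (both assumed).

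- Planned 20 per arm: about 9% (δ 5, σ 25) to 56% (δ 10, σ 15).
- Completers, 3 vs 3 or 3 vs 9: about 4% to 17%.

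The reported data can neither show nor exclude a diary effect of this order.

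**The case against.** The strongest reply is that hygiene is looked after in every arm. All subjects get repeated instruction with disclosed plaque as the check, MQH is scored by a blinded examiner, and the report sees no obvious plaque difference between arms. This stands against the broader inference that brushing goes unmonitored in the SRP arm: only the diary is unequal. It does not equalize daily self-recording, and a descriptive statement about 3, 3 and 9 completers cannot exclude a difference.

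A reader might also infer that the bleeding results are in fact biased toward gel. The documents do not support that. The week 0–4 changes are inconsistent between two identically managed arms, and no diary effect is reported. Nor do they say clearly that diaries were reviewed at every visit.

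A reader might set the assumed 2 to 5 points against the raw week-26 gaps, 44 − 33 = 11 and 44 − 28 = 16, and obtain 18–45% and 13–31%. Baseline BOP differed widely (45, 57 and 63.1%), and the plan uses baseline data with ANCOVA, so change from baseline is the fairer denominator. It roughly halves those shares.

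Finally, a formal MQH comparison might seem to resolve the matter. It would not: the Introduction says topical peroxide itself reduces plaque, so a difference could come from gel or diary, and a null result at these numbers would be uninformative.

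**Conclusion.** The point holds as an avoidable asymmetry between arms. On the natural reading, diary self-monitoring of brushing is confined to the gel groups in a trial where patients know their arm, and it bears on a primary outcome. Bias toward gel is a plausible risk that has not been demonstrated.

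On an assumed effect of 2 to 5 BOP points, it would account for about 9–22% of the HP13 and 6–15% of the HP26 difference from SRP. It would therefore not explain most of either reported difference. The estimate depends on the assumed effect, on reading 28% as HP26, and on means from 15 completers. The case for acting is that the difference is unnecessary and almost free to remove.

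The week-0 OHI listing is a second possible asymmetry in the same direction. It conflicts with Therapy Phase and Standardized OHI, so the documents do not establish whether it occurred.

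**What to change.** **In the plan.** Either give the SRP arm the same brushing calendar from week 0, without the tray column and with the same review, or limit the gel-arm journal to tray use. The first keeps brushing data in all arms; the second removes the co-intervention. State when diaries are reviewed.

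**Reconcile the text.** Therapy Phase (tray use only) and Custom HP Tray Application (brushing as well) must agree. So must the week-0 OHI entries for the two schedules in Study Schedule, against Therapy Phase and Standardized OHI.

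**For data already collected.** State the unequal diary as a limitation. Report MQH by arm and visit with patient-level estimates and confidence intervals, as description only: follow-up MQH is measured after randomization and peroxide may itself affect it, so it cannot separate a diary effect from a gel effect.

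**Cost.** Paper calendars for one arm and a few minutes per visit; the second option costs nothing beyond a change to the journal form.
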